7.2 Immune Related Response Criteria

As a secondary endpoint, this study will evaluate concordance of the Immune Related Response Criteria (irRC) with RECIST 1.1. These response criteria were developed to overcome the variable and unusual patterns of response to immunotherapeutic agents, in particular, ipilimumab. The development of the guidelines was prompted by observations, mostly in subjects with metastatic melanoma, of initial disease progression followed by later response, late responses, and mixed responses with an overall decrease in tumor burden.

Antitumor response based on total measurable tumor burden

For the irRC, only index and measurable new lesions are taken into account (in contrast to conventional WHO criteria, which do not require the measurement of new lesions, nor do they include new lesion measurements in the characterization of evolving tumor burden). At the baseline tumor assessment, the sum of the products of the two largest perpendicular diameters (SPD) of all index lesions (5 lesions per organ, up to 10 visceral lesions) is calculated. At each subsequent tumor assessment, the SPD of the index lesions and of new, measurable lesions (up to 5 new lesions per organ; 10 visceral lesions) are added together to provide the total tumor burden:

Tumor Burden = SPD_{index lesions} + SPD_{new, measurable lesions}

Table: Comparison of WHO and irRC criteria

	WHO	irRC
New, measurable lesions	Always represent PD	Incorporated into tumor burden
New, nonmeasurable lesions	Always represent PD	Do not define progression (but preclude irCR)
Non-index lesions	Changes contribute to defining BOR of CR, PR, SD, and PD	Contribute to defining irCR (complete disappearance required)
CR	Disappearance of all lesions in two consecutive observations not less than 4 wk apart	Disappearance of all lesions in two consecutive observations not less than 4 wk apart
PR	≥50% decrease in SPD of all index lesions compared with baseline in two observations at least 4 wk apart, in absence of new lesions or unequivocal progression of non-index lesions	≥50% decrease in tumor burden compared with baseline in two observations at least 4 wk apart
SD	50% decrease in SPD compared with baseline cannot be established nor 25% increase compared with nadir, in absence of new lesions or unequivocal progression of non-index lesions	50% decrease in tumor burden compared with baseline cannot be established nor 25% increase compared with nadir
PD	At least 25% increase in SPD compared with nadir and/or unequivocal progression of non-index lesions and/or appearance of new lesions (at any single time point)	At least 25% increase in tumor burden compared with nadir (at any single time point) in two consecutive observations at least 4 wk apart

Time-point response assessment using irRC

Percentage changes in tumor burden per assessment time point describe the size and growth kinetics of both conventional and new, measurable lesions as they appear. At each tumor assessment, the response in index and new, measurable lesions is defined based on the change in tumor burden (after ruling out irPD). Decreases in tumor burden must be assessed relative to baseline measurements (i.e., the SPD of all index lesions at screening). The irRC were derived from WHO criteria and, therefore, the thresholds of response remain the same. However, the irRC response categories have been modified from those of WHO criteria.

Overall response using the irRC

The sum of the products of diameters at tumor assessment using the immune-related response criteria (irRC) for progressive disease incorporates the contribution of new measurable lesions. Each net Percentage Change in Tumor Burden per assessment using irRC criteria accounts for the size and growth kinetics of both old and new lesions as they appear.

Definition of Index Lesions Response Using irRC

- **irComplete Response (irCR):** Complete disappearance of all *index* lesions. This category encompasses exactly the same subjects as “CR” by the mWHO criteria.
- **irPartial Response (irPR):** Decrease, relative to baseline, of 50% or greater in the sum of the products of the 2 largest perpendicular diameters of all

index and all new measurable lesions (ie, Percentage Change in Tumor Burden). **Note:** the appearance of new measurable

- **irStable Disease (irSD):** Does not meet criteria for irCR or irPR, in the absence of progressive disease.
- **irProgressive Disease (irPD):** At least 25% increase Percentage Change in Tumor Burden (i.e., taking sum of the products of all *index* lesions and any new lesions) when compared to SPD at nadir.

Definition of Non-Index Lesions Response Using irRC

- **irComplete Response (irCR):** Complete disappearance of all *non-index* lesions. This category encompasses exactly the same subjects as “CR” by the mWHO criteria.
- **irPartial Response (irPR) or irStable Disease (irSD):** *non-index* lesion(s) are not considered in the definition of PR, these terms do not apply.
- **irProgressive Disease (irPD):** Increases in number or size of *non-index* lesion(s) does not constitute progressive disease unless/until the Percentage Change in Tumor Burden increases by 25% (i.e., the SPD at nadir of the *index* lesions increases by the required amount).

Impact of New Lesions on irRC New lesions in and by themselves do not qualify as progressive disease. However, their contribution to total tumor burden is included in the SPD, which in turn feeds into the irRC criteria for tumor response. Therefore, new non-measurable lesions will not discontinue any subject from the study.

Definition of Overall Response Using irRC

Overall response using irRC will be based on these criteria:

- **Immune-Related Complete Response (irCR):** Complete disappearance of *all* tumor lesions (*index* and *non-index* together with no new measurable/unmeasurable lesions) for at least 4 weeks from the date of documentation of complete response.
- **Immune-Related Partial Response (irPR):** The sum of the products of the two largest perpendicular diameters of all *index* lesions is measured and captured as the SPD baseline. At each subsequent tumor assessment, the sum of the products of the two largest perpendicular diameters of all *index* lesions and of new measurable lesions are added together to provide the Immune Response Sum of Product Diameters (irSPD). A decrease, relative to baseline of the irSPD compared to the previous SPD baseline, of 50% or greater is considered an immune Partial Response (irPR).
- **Immune-Related Stable Disease (irSD):** irSD is defined as the failure to meet criteria for immune complete response or immune partial response, in the absence of progressive disease.
- **Immune-Related Progressive Disease (irPD):** It is recommended in difficult cases to confirm PD by serial imaging. Any of the following will constitute progressive disease:
 - At least 25% increase in the sum of the products of all *index* lesions over nadir SPD calculated for the *index* lesions.
 - At least a 25% increase in the sum of the products of all *index* lesions and new measurable lesions (irSPD) over the baseline SPD calculated for the *index* lesions.
- **Immune-Related Best Overall Response Using irRC (irBOR)** irBOR is the best confirmed irRC overall response over the study as a whole, recorded between the date of first dose until the last tumor assessment before subsequent therapy (except for local palliative radiotherapy for painful bone lesions) for the individual subject in the study. For the assessment of irBOR, all available assessments per subject are considered. irCR or irPR determinations included in the irBOR assessment must be confirmed by a second (confirmatory) evaluation meeting the criteria for response and performed no less than 4 weeks after the criteria for response are first met.

Derivation of irRC overall responses

Measurable Response	Nonmeasurable Response		Overall Response
Index and new, measurable lesions (tumor burden),*%	Non-index lesions	New, non-Measurable lesions	Using irRC
↓100	Absent	Absent	irCR†
↓100	Stable	Any	irPR†
↓100	Unequivocal Progression	Any	irPR†
↓≥50	Any/Stable	Any	irPR†
↓≥50	Unequivocal Progression	Any	irPR†
↓<50 to <25↑	Any/Stable	Any	irSD
↓<50 to <25↑	Unequivocal Progression	Any	irSD
25	Any	Any	irPD†

*Decreases assessed relative to baseline (scan prior to start of any protocol therapy), including measurable lesions only

†Assuming response (irCR) and progression (irPD) are confirmed by a second, consecutive assessment at least 4 wk apart.

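### For patients with new measurable lesions, Section 7.2 gives conflicting irPD rules, so one scan can receive different irRC categories and irRC PFS can be dated differently.

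*Combined protocol and SAP*

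**What the plan says.** The relevant definitions are in protocol Section 7.2. It first defines tumour burden as the sum of products of diameters (SPD) of the index lesions plus that of new measurable lesions. Progression is then stated several times:

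- **Comparison table, irRC column, PD row:** "At least 25% increase in tumor burden compared with nadir (at any single time point) in two consecutive observations at least 4 wk apart".
- **Same column, SD row:** "50% decrease in tumor burden compared with baseline cannot be established nor 25% increase compared with nadir".
- **Definition of Index Lesions Response:** a rise of at least 25% in a sum that includes any new lesions, "when compared to SPD at nadir".
- **Definition of Overall Response:** "Any of the following will constitute progressive disease", then two limbs, each needing a 25% rise. Limb 1 is index "lesions over nadir SPD calculated for the" index lesions. Limb 2 is index "lesions and new measurable lesions (irSPD) over the baseline SPD calculated for the" index lesions.
- **Derivation table:** its footnote takes baseline as the reference for decreases and gives none for increases.

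Sections 2.4 and 11.1 make best response and PFS by irRC secondary endpoints. Section 11.2 plans medians and Kaplan-Meier plots under RECIST and irRC separately, and Section 7.2 adds concordance between the two. The PFS definition in Section 7.1 runs to progression or death and does not say which irPD rule supplies the date.

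**The concern.** For the same quantity, index plus new measurable lesions, the table and the index-lesion definition use nadir as the reference, while limb 2 of the overall-response definition uses the pre-treatment value. Section 7.2 assigns response categories only once irPD has been excluded, so the reference point decides the category. With no order of precedence stated, two analysts following the protocol could give one patient different irRC event statuses or dates, and the rule could be settled after the scans have been seen. Follow-up imaging is every 12 weeks (Section 5.8), so one changed call there can move an irRC PFS event by about 12 weeks.

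**Working it through.** The plan states no figure to reproduce. The check applies both rules to the same scans.

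**Notation.** I = index SPD, N = SPD of new measurable lesions, B = I + N.

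- **Nadir rule** (table and index-lesion definition): irPD if B ≥ 1.25 × lowest earlier B.
- **Overall-response rule:** irPD if I ≥ 1.25 × lowest earlier I (limb 1), or if B ≥ 1.25 × baseline I (limb 2).
- If not irPD: irPR when B ≤ 50% of baseline, otherwise irSD.

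**Assumptions.** Baseline I = 100 in arbitrary units. Baseline can itself be the nadir. Each scan is classified alone, leaving confirmation aside. The scan values are hypothetical.

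**No new measurable lesions.** Then B = I and the nadir rule is identical to limb 1. Limb 2 adds nothing, because the nadir cannot exceed baseline. The rules agree.

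| Case | Scans (index + new) | Nadir rule | Overall-response rule |
|---|---|---|---|
| A | 100; 40; 60 | 60/40 − 1 = +50%: irPD | limb 1, +50%: irPD |
| B | 100; 40; 40 + 20 | 60/40 − 1 = +50%: irPD | index 0%; 60/100 − 1 = −40%: irSD |
| C | 100; 30; 30 + 10 | 40/30 − 1 = +33.3%: irPD | index 0%; 40/100 − 1 = −60%: irPR |
| D | 100; 40 + 40; 50 + 20 | 70/80 − 1 = −12.5%: irSD | limb 1, 50/40 − 1 = +25%: irPD |
| E | 100; 100; 100 + 25 | +25%: irPD | limb 2, +25%: irPD |

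Cases B and C are irPD only under the nadir rule. Case D is irPD only under the overall-response rule.

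**Width of the conflict.** Hold the index lesions at nadir n and put all growth in new lesions. The nadir rule triggers at B = 1.25n. Limb 1 never triggers, and limb 2 triggers at B = 125. The rules therefore disagree for 1.25n ≤ B < 125:

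- n = 90: 112.5 up to 125
- n = 80: 100 up to 125
- n = 50: 62.5 up to 125
- n = 40: 50 up to 125

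At n = 100 (no shrinkage) the lower limit is itself 125 and the window closes.

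**Best response.** Section 7.2 requires irPR to be confirmed by a second evaluation at least four weeks later. In case C, if the scan at 30 is the first to show irPR, the next scan confirms it under the overall-response rule but is irPD under the nadir rule. Best response can then differ. In case B, if the fall to 40 had already been confirmed, best response is irPR under both.

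**Confirmation of irPD.** The table's PD row requires two observations in a row, four or more weeks apart, and the derivation-table footnote assumes the same. The index-lesion definition asks for no confirmation. The overall-response definition only advises it for difficult cases. No text says whether the first or the confirming scan dates the irRC PFS event.

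**The case against.** The best defence is that there is no real conflict, because the overall-response definition governs. Its heading and opening sentence say that overall response rests on its criteria, the comparison table contrasts two systems, and the index-lesion definition covers a component. This is a fair reading, but not a conclusive one. The table's irRC column and the index-lesion definition are written as rules for irPD. The derivation table for overall response works from total burden and leaves the reference for increases open. No precedence is stated. What stands is that the documents do not select the nadir rule either, so preferring it is a choice made for consistency.

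A reader might infer that the overall-response rule is baseline-based throughout, so that any patient who shrinks first can progress substantially without an irPD call. The text does not support that: limb 1 compares index lesions with their nadir, so regrowth of index lesions is caught (case A). A missed call needs new measurable lesions, an earlier fall below baseline, and index lesions less than 25% above their nadir.

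A reader might also infer that the overall-response wording can only delay events and lengthen irRC PFS. Case D shows the opposite.

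On weight, the irRC analyses are descriptive and no decision depends on them. RECIST PFS is reported separately and counts any new lesion as progression, so such patients remain visible. That stands and limits the importance of the point.

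**Conclusion.** Wrong as written, with limited reach. For patients with new measurable lesions, Section 7.2 contains irPD rules that can classify the same scan as irPD or irSD, as irPD or irPR, or as irSD or irPD. In the frozen-index setting the disagreement is wide after a deep response (50 up to 125 for nadir 40) and narrow after a slight one (112.5 up to 125 for nadir 90). It affects irRC PFS and irRC-RECIST concordance, and best response by irRC in some sequences. The primary feasibility endpoint and the sample size of 20 are untouched.

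These sizes rest on hypothetical scans. The documents give no rate of new measurable lesions after shrinkage, so the number of affected patients cannot be estimated. It would also go too far to infer that adopting the index-lesion wording makes irRC PFS well defined, since confirmation and the event date would remain open.

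**What to change.** Reconcile the irPD statements in Section 7.2 so that one rule is used to derive irRC best response, irRC PFS and concordance. The rule that matches the protocol's own tumour-burden definition, and is stated most often, is a rise of at least 25% in index plus new measurable burden over the nadir burden. If the sponsor prefers the overall-response wording, the table and the index-lesion definition need to be aligned with it.

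In the same edit:

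- state one confirmation requirement for irPD in the analysis;
- state whether the first or the confirming scan dates the irRC PFS event;
- give the reference point for increases in the derivation table.

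Limit this change to endpoint derivation. Section 5.6 ties the duration of treatment to the progression definitions in Section 7.0, which include Section 7.2, and also allows treatment past first imaging progression. The sponsor must reconcile separately which definition applies there; no clinical rule is proposed.

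The cost is wording only, with no new data. If the nadir rule is adopted, some irRC PFS times may be shorter (cases B and C) and some longer (case D) than under the overall-response wording. The edit is best made before irRC results are examined.

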5.6 Duration of Therapy

In the absence of treatment delays due to adverse events, treatment will continue for 17 cycles or until one of the following criteria apply:

- Disease progression as defined in Section 7.0
- Patients may continue on pembrolizumab beyond the first progression by imaging as long as investigator deemed clinical benefit continues
- Inter-current illness that prevents further administration of treatment
- Unacceptable adverse event(s) or death
- Patient voluntarily withdraws from treatment
- General or specific changes in the patient's condition render the patient unacceptable for further treatment in the judgment of the investigator

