5.8 Duration of Follow-Up

Continued follow-up after end of treatment is for patients who discontinue study treatment for reasons other than progressive disease or death (such as patients who discontinue treatment due to toxicity) AND patients who continue on treatment past 17 cycles. These patients should continue to be followed by imaging every 12 weeks with standard of care CT chest, abdomen/pelvis until documentation of progressive disease, death, withdrawal of consent, or initiation of a new anti-cancer treatment for up to 2 years.

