Note: If subjects respond to treatment and are able to have their disease resected, the patient’s response will be assessed prior to the surgery.

Duration of Response

Duration of overall response: The duration of overall response is measured from the time measurement criteria are met for CR or PR (whichever is first recorded) until the first date that recurrent or progressive disease is objectively documented (taking as reference for progressive disease the smallest measurements recorded since the treatment started).

The duration of overall CR is measured from the time measurement criteria are first met for CR until the first date that recurrent disease is objectively documented.

Duration of stable disease: Stable disease is measured from the start of the treatment until the criteria for progression are met, taking as reference the smallest measurements recorded since the treatment started.

Progression-Free Survival

Progression-free survival (PFS) is defined as the duration of time from start of treatment to time of progression or death, whichever occurs first. Patients without progression or death will be censored at the date of their last scan.

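### Section 7.2 gives two conflicting irPD rules, and nothing says how irRC progression-free survival treats an irPD that is never confirmed

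*Combined protocol and SAP*

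**What the plan says.** Section 7.2 states the irPD rule in three places.

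- **WHO/irRC comparison table:** "At least 25% increase in tumor burden compared with nadir (at any single time point) in two consecutive observations at least 4 wk apart".
- **Definition of Overall Response Using irRC:** "It is recommended in difficult cases to confirm PD by serial imaging". It continues "Any of the following will constitute progressive disease" and lists 25% increases, with no second observation required.
- **Footnote to the derivation table:** "Assuming response (irCR) and progression (irPD) are confirmed by a second, consecutive assessment at least 4 wk apart".

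Three other provisions decide what happens to a patient at first irPD.

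- **Imaging after treatment** (5.8, repeated in 6.1 and in footnote 5 of the 6.2 calendar): "Continued follow-up after end of treatment is for patients who discontinue study treatment for reasons other than progressive disease or death", and also for patients treated past 17 cycles. For this group, "These patients should continue to be followed by imaging every 12 weeks".
- **Treatment after progression** (5.6): "Patients may continue on pembrolizumab beyond the first progression by imaging as long as investigator deemed clinical benefit continues".
- **Censoring** (7.1, Progression-Free Survival): "Patients without progression or death will be censored at the date of their last scan".

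Section 11.2 describes PFS by Kaplan-Meier, separately for RECIST and irRC. It does not define the irRC event, date a confirmed irPD, or say what to do with an irPD that has no later scan.

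**The concern.** The two irPD rules define different events for the same secondary endpoint, and an analyst could defend either one. The choice matters because of the imaging schedule. Under the confirmation rule, a patient who leaves treatment at first irPD has no planned scan that could supply the confirmation. That patient then has no confirmed event, and the last scan is the one that showed progression. Censoring there is informative: the patient leaves the risk set because of the event being measured. The bias can only be upward.

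At stake is the comparison that 7.2 sets up between irRC and RECIST 1.1. irPFS could exceed RECIST PFS because confirmation scans are missing, and the gap could be read as an immune-type pattern of benefit.

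**Working it through.** **Plan's own figure.** The documents give no design figure for irPFS, so there is nothing to reproduce on this endpoint. The one computed design figure, 14/20 = 70% (50%–90%) in 11.1, reproduces as 0.70 ± 1.96 × √(0.7 × 0.3/20) = 49.9% to 90.1%. It plays no part in this point.

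**Path of a patient at first irPD**

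| Situation | Single-scan rule | Confirmation rule |
|---|---|---|
| Continues pembrolizumab (5.6) and a later scan confirms | Event | Event |
| Stops for progression, no later scan (5.8, 6.1) | Event | No confirmed event; last scan is the irPD scan |

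Only the second row differs, and it produces the bias.

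**Inputs.** From the documents: 20 patients, a scan at week 12, off-treatment imaging every 12 weeks, and death as a PFS event. Assumed:

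- 12-weekly scans throughout;
- exponential time to first event with median *m* = 13 weeks (range 9 to 18);
- a share *d* of first events that are deaths (0 or 0.15), always counted;
- a share *q* of progressors with no later scan (0 to 1), censored at the irPD scan.

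**Formula.** The chance of passing one 12-week interval event-free is s = 2^(−12/m). Patients censored at a scan are still at risk at that scan, so the Kaplan-Meier curve is multiplied per interval by

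f = 1 − (1 − s) × [1 − q(1 − d)],

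and the 24-week estimate is f².

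**Worked case, m = 13.** s = 2^(−12/13) = 0.5274, so 1 − s = 0.4726.

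- Every first irPD counted (q = 0): f = 0.5274; f² = **0.28**.
- q = 0.5, d = 0.15: f = 1 − 0.4726 × 0.575 = 0.7283; f² = **0.53**.
- q = 0.5, d = 0: f = 1 − 0.4726 × 0.5 = 0.7637; f² = **0.58**. Simulated trials of 20 patients give 0.58 to 0.59.

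**Range, d = 0.15, for true medians of 9 / 13 / 18 weeks.** The 24-week values come from the formula, and simulation agrees within 0.01. Medians and event counts come from a simulation of 200,000 patients with a 96-week cut-off.

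| q | 24-week irPFS | Kaplan-Meier median (weeks) | Expected events of 20 |
|---|---|---|---|
| 0 | 0.16 / 0.28 / 0.40 | 12 / 20 / 24 | 20.0 / 19.9 / 19.5 |
| 0.25 | 0.28 / 0.39 / 0.50 | 18 / 24 / 25 | 15.8 / 15.6 / 15.4 |
| 0.50 | 0.43 / 0.53 / 0.62 | 24 / 34 / 36 | 11.5 / 11.5 / 11.2 |
| 0.75 | 0.61 / 0.69 / 0.75 | 36 / 48 / 60 | 7.3 / 7.2 / 7.1 |

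Under the single-scan rule the q = 0 row applies whatever the share without a later scan.

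**The case against.** The other side has several good points.

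- **The single-scan wording may be the operative one.** It sits in the definition of overall response. The index-lesion irPD definition also asks for no confirmation, and the irBOR text requires it for irCR and irPR without naming irPD. On that reading the bias is zero. This stands, so a reader may not infer that irPD must be confirmed. But two tables say otherwise, one of them the table that derives the overall response.
- **The censoring rule was written under RECIST** and covers patients without progression. Applying it to an unconfirmed irPD is an inference, and an analyst could instead count the first irPD. This also stands. But it is the only PFS censoring rule in the documents; if it does not apply, irPFS has none.
- **Treatment beyond progression supplies later scans.** It does for some patients. A reader might infer that many irPFS events would be lost, but the documents give no share who stop at first irPD, so that is unsupported. Nor do they show that the share is small, since continuation is at the investigator's judgement.
- **Deaths limit the damage.** They do, if captured, although patients who stop for progression are outside the described follow-up. A reader might infer that the irPFS median would usually not be reached. With 75% lacking a later scan, that happens in over half of simulated trials only if no first event is a death. With 15% deaths it is about a quarter (24–26%; 21–38% across variants).

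The study calendar is also hard to read in the available text. One imaging mark may belong to the end-of-treatment visit, but a scan there would confirm irPD only if taken at least 4 weeks after the first.

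**Conclusion.** The firm finding is an inconsistency: 7.2 contains two incompatible irPD rules, and neither 7.2 nor 11.2 settles the irPFS event. The upward bias is conditional. It arises if the confirmation rule is used and the 7.1 censoring rule is carried over to irRC, and it falls on patients who stop at first irPD with no later scan.

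Under those conditions it can be large. In the 13-week case with half of progressors lacking a later scan, 24-week irPFS is overstated by about 25 percentage points with 15% deaths, or about 30 with none. With the deaths included, the median moves from 20 to 34 weeks. These sizes rest on assumed medians, death shares and values of q; the documents supply none of them.

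The consequence is limited. irPFS is secondary and descriptive, with no hypothesis or decision attached. The 14/20 feasibility rule and RECIST PFS are unaffected; the irRC/RECIST comparison is affected only under the confirmation reading. The change is worth making before analysis, but the trial's main conclusion does not depend on it.

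**What to change.** Reconcile the three statements of the irPD rule in 7.2, then state one irPFS event rule there and in 11.2:

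- A confirmed irPD is an event dated at its first observation.
- A first irPD with no later evaluable scan, for whatever reason, is an event on the date of that first irPD and is not censored.
- A first irPD that a later scan does not confirm is not an event; follow-up for irPFS continues.
- A confirmed-only version, with unconfirmed irPD censored, is reported as a sensitivity analysis, together with the number of patients whose first irPD had no later scan.

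The cost is wording only, with no extra scans and no change to patient care. There is a real downside. Some possible pseudoprogression without a later scan will be counted as an event. irPFS will also be less favourable than under the confirmed-only reading, possibly by much more than a little. The sensitivity analysis and the reported count let a reader judge both. Other conventions can be defended; the need is to fix one in advance.
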